10.4 Study Conduct

The investigator agrees that the study will be conducted according to the principles of ICH E6(R2). The investigator will conduct all aspects of this study in accordance with all national, state, and local laws or regulations. Study information from this protocol will be posted on publicly available clinical trial registers before the enrollment of subjects begins.

10.5 Adherence to Protocol

The investigator agrees to conduct the study as outlined in this protocol in accordance with ICH E6(R2) and all applicable guidelines and regulations.

10.6 Adverse Events and Study Report Requirements

By participating in this study the investigator agrees to submit reports of SAEs to the sponsor and/or IRB according to the timeline and method outlined in the protocol. In addition, the investigator agrees to submit annual reports to the study site IRB as appropriate.

10.7 Investigator's Final Report

Upon completion of the study, the investigator, where applicable, should inform the institution; the investigator/institution should provide the IRB with a summary of the study's outcome and the sponsor and regulatory authority(ies) with any reports required.

10.8 Records Retention

Essential documents should be retained until at least 2 years after the last approval of a marketing application in an ICH region and until there are no pending or contemplated marketing applications in an ICH region or at least 2 years have elapsed since the formal discontinuation of clinical development of the investigational product. These documents should be retained for a longer period, however, if required by the applicable regulatory requirements or by an agreement with the sponsor. It is the responsibility of the sponsor to inform the investigator/institution as to when these documents no longer need to be retained.

10.9 Publications

After completion of the study, the data may be considered for reporting at a scientific meeting or for publication in a scientific journal. In these cases, the sponsor will be responsible for these activities and will work with the investigators to determine how the manuscript is written and edited, the number and order of authors, the publication to which it will be submitted, and other related issues. The sponsor has final approval authority over all such issues.

The data are the property of the sponsor and cannot be published without prior authorization from the sponsor, but data and publication thereof will not be unduly withheld.

11 Study Management

11.1 Monitoring

11.1.1 External Data Monitoring Committee

There will not be an external data monitoring committee for this study.

11.1.2 Monitoring of the Study

The medical monitor, as a representative of the sponsor, has the obligation to follow the study closely.

The study monitor will visit the investigator and study site at periodic intervals, in addition to maintaining necessary telephone and letter contact. The study monitor will maintain current personal knowledge of the study through observation, review of study records and source documentation, and discussion of the conduct of the study with the investigator and personnel.

All aspects of the study will be carefully monitored, by the sponsor or its designee, for compliance with applicable government regulation with respect to current GCP and current standard operating procedures.

11.1.3 Inspection of Records

Investigators and institutions involved in the study will permit study-related monitoring, audits, IRB review, and regulatory inspections by providing direct access to all study records. In the event of an audit, the investigator agrees to allow the sponsor, representatives of the sponsor, or a regulatory agency access to all study records.

The investigator should promptly notify the sponsor and [REDACTED] of any audits scheduled by any regulatory authorities and promptly forward copies of any audit reports received to the sponsor.

11.2 Management of Protocol Amendments and Deviations

11.2.1 Modification of the Protocol

Any changes in this research activity, except those necessary to remove an apparent immediate hazard to the subject, must be reviewed and approved by the sponsor or its designee. Amendments to the protocol must be submitted in writing to the investigator's IRB for approval before subjects can be enrolled into an amended protocol.

11.2.2 Protocol Deviations

The investigator or designee must document and explain in the subject's source documentation any deviation from the approved protocol. The investigator may implement a deviation from, or a change of, the protocol to eliminate an immediate hazard to study subjects without prior IRB approval. As soon as possible after such an occurrence, the implemented deviation or change, the reasons for it, and any proposed protocol amendments should be submitted to the IRB for review and approval, to the sponsor for agreement, and to regulatory authorities, if required.

A deviation from the protocol is an unintended or unanticipated departure from the procedures or processes approved by the sponsor and the IRB and agreed to by the investigator. A significant deviation occurs when there is nonadherence to the protocol by the subject or investigator that results in a significant additional risk to the subject. Significant deviations can include nonadherence to inclusion or exclusion criteria or nonadherence to FDA regulations or ICH GCP guidelines and will lead to the subject being withdrawn from the study (Section 4.2).

Protocol deviations will be documented by the clinical monitor throughout the course of monitoring visits. Principal investigators will be notified of deviations in writing by the monitor. The IRB should be notified of all protocol deviations in a timely manner.

11.3 Study Termination

Although Ovid has every intention of completing the study, Ovid reserves the right to discontinue the study at any time for clinical or administrative reasons.

The end of the study is defined as the date on which the last subject completes his last visit (includes follow-up visit).

MedDRA	Medical Dictionary for Regulatory Activities
mg	Milligram
mmHg	Millimeter of mercury
MMRM	Mixed Model with Repeated Measures
PD	Pharmacodynamic(s)
PedsQL	Pediatric Quality of Life Inventory
PGI-I	Parent Global Impressions-Improvement
PGI-S	Parent Global Impressions-Severity
[REDACTED]	[REDACTED]
PT	Preferred Term
Q1	1 st Quartile
Q3	3 rd Quartile
QD	Once a Day
RBANS	Repeatable Battery for the Assessment of Neuropsychological Status
RBS-R	Repetitive Behavior Scale-Revised
SAE	Serious Adverse Event
SAP	Statistical Analysis Plan
SAS	Statistical Analysis System

SB-5	Stanford-Binet-5
SD	Standard Deviation
SI	International System
SOC	System Organ Class
SOL	Sleep Onset Latency
TEAE	Treatment-Emergent Adverse Event
TID	Three Times a Day
TST	Total Sleep Time
VABS-3	Vineland Adaptive Behavior Scale, 3 rd Edition
WASO	Wake Time After Sleep Onset

1. INTRODUCTION

Fragile X syndrome (FXS) is the most common inherited form of intellectual disability, with a prevalence of 1 in 4000 males and 1 in 8000 females (Crawford et al 2001). It is also the most common known genetic cause of autism; approximately 25% to 30% of individuals with FXS meet the full diagnostic criteria for autism, and approximately 5% of children with autism carry the fragile X mutation (Hall et al 2008; Harris et al 2008). Males with FXS have moderate to severe intellectual disability, and females with FXS range from normal to moderate impairment (Hagerman et al 2010).

OV101 is the first highly selective, extrasynaptic gamma-aminobutyric acid (GABA) receptor agonist that binds as an orthosteric agonist to the $\alpha 4$ - and δ -containing subunit of extrasynaptic GABA receptors. The mechanism of action of OV101 is unique among GABAergic agents, including benzodiazepines, zolpidem and other zolpidem-like drugs, neurosteroids, and drugs that act on GABA metabolism or uptake.

The use of OV101 for treatment of individuals with FXS is based on studies in a relevant mouse model of the disease, the *Fmr1* knockout (KO) mouse, which lacks the fragile X mental retardation protein due to a disruption in its *FMR1* gene. *Fmr1* KO mice have decreased GABA synthesis, decreased presynaptic GABA release, and decreased extrasynaptic levels of GABA, resulting in decreased tonic inhibition. OV101 was shown to restore tonic inhibition in the amygdala, reduce sensory hypersensitivity and motor hyperactivity, and improve pre-pulse inhibition (signal to noise ratio) in *Fmr1* KO mice. Cogram et al recently presented data that showed full normalization of abnormal repetitive, social, and anxiety-like behaviors with OV101 in another FXS KO mouse model, the *Fmr1* KO2 mouse. Taken together, these data support the potential of OV101 to treat the core behavioral deficits noted in individuals with FXS. Importantly, the ability of OV101 to potentiate tonic inhibition is unlike any other GABAergic agent, including benzodiazepines, zolpidem, other zolpidem-like drugs, neurosteroids, and drugs that act on GABA metabolism or uptake.

Phase 2 and Phase 3 studies in adult subjects with primary insomnia demonstrated that OV101 is effective in restoring classical sleep parameters (sleep induction and sleep maintenance) and slow wave sleep, resulting in an improvement in the quality and restorative effects of sleep.

This Statistical Analysis Plan (SAP) describes the data-handling and statistical procedures to be used for the statistical analysis and reporting of efficacy and safety data collected under the Ovid Protocol OV101-17-001 Amendment #2 (March 27, 2019). The methods of analysis in this SAP expand on statistical considerations identified in the protocol; where considerations are substantially different, they will be identified as such in this document. This SAP has been developed and finalized prior to locking the clinical database for the primary analysis. Any additional analyses required to supplement the analyses specified in this SAP will be considered exploratory and will be identified in the Clinical Study Report (CSR).

The SAP was written in accordance with the recommendations outlined in the International Conference on Harmonisation (ICH) E9 Guideline entitled “Guidance for Industry: Statistical Principles for Clinical Trials” and the most recent ICH-E3 Guideline entitled “Guidance for Industry: Structure and Content of Clinical Study Reports.”

2. OBJECTIVES

2.1. Primary Objective

[figure not shown]
- To evaluate the safety and tolerability of OV101 over 12 weeks of treatment across different daily dosing regimens in adolescent and adult male subjects with FXS.

2.2. Secondary Objectives

[figure not shown]
- To evaluate changes in behavior during 12 weeks of treatment with OV101 across different daily dosing regimens in adolescent and adult male subjects with FXS

2.3. Exploratory Objectives

- To evaluate changes in sleep, adaptive functioning, and quality of life across different daily dosing regimens of OV101 treatment over 12 weeks in adolescent and adult male subjects with FXS

- To explore the relationships among study endpoints (e.g., behavior, sleep), where appropriate

[figure not shown]

3. INVESTIGATIONAL PLAN

3.1. Overall Study Design and Plan

This is a Phase 2a, randomized, double-blind, parallel-group study to evaluate the safety, tolerability, and efficacy of OV101 administered daily as 3 different dosing regimens: 5 mg/day (5 mg QD), 10 mg/day (5 mg BID), and 15 mg/day (5 mg TID) in adolescent and adult male subjects with FXS. Subjects with a clinically and molecularly confirmed diagnosis of FXS will be eligible for inclusion in the study (Section 4.1 of the protocol). The study will comprise a screening period of up to 3 weeks; a baseline visit on Day 1 for treatment randomization (enrollment), baseline assessments, and first dose of study drug; clinic visits for safety and efficacy assessments over a 12-week treatment period, including clinic visits at Week 2, Week 6, and Week 12 (end-of-treatment [EOT]); and an end-of-study (EOS) follow-up visit occurring any time between the ends of Week 16 and Week 18 (Figure 1). The schedule of study procedures is presented in [Section 13.5](#).

Figure 1 Study Schematic

For each subject, after informed consent is obtained (Section 9.3 of the protocol), screening assessments will be completed within the 3 weeks preceding Baseline. At Baseline, subjects 13 to 22 years old (inclusive) who meet all eligibility criteria (Section 4.1 of the protocol) will be enrolled on Day 1 in a 1:1 target ratio between adolescents (13 to 17 years old, inclusive) and adults (18 to 22 years old, inclusive). A sufficient number of subjects will be enrolled to ensure that at least 30 evaluable subjects complete 12 weeks of treatment.

Subjects will be randomly assigned in a 1:1:1 ratio to 1 of 3 treatment groups (5 mg QD, 5 mg BID, and 5 mg TID), stratified by age group (adolescent/adult) to achieve balance among treatment arms. There is no placebo group in this study. All subjects will take study drug TID (morning, afternoon, and evening), OV101 in the morning and OV101 or placebo in the afternoon and evening throughout the treatment period (including Baseline), as described in Section 5.2 and Section 5.4.1 of the protocol. There will not be any dose adjustments permitted during the study.

After random assignment at Baseline, subjects will receive the assigned package of blinded study treatment according to the treatment code for the first 6 weeks of treatment and will take their first dose of study drug at the clinic. They will receive another assigned package of study treatment at the Week 6 clinic visit.

Each subject (assisted by a legally acceptable representative [LAR]/caregiver) will complete paper sleep diaries and wear actigraphs over the 7-day periods immediately preceding Baseline and the Week 2, Week 6, EOT, and EOS clinic visits. The Baseline, Week 2, Week 6, and EOT visits will be full-day clinic visits.

For each subject, after informed consent is obtained, the maximum duration of individual subject participation will be 21 weeks. A subject will have completed the study when he completes the EOS visit. The end of the study is defined as the date when the last subject completes his last visit (includes follow-up visit).

Safety information will be collected during phone calls at the end of Weeks 1, 4, 8, and 10 (on Days 8, 29, 57, and 71, respectively), in addition to during every clinic visit (screening, baseline, Week 2, Week 6, EOT, and EOS). At the investigator's discretion, subjects may be evaluated at unscheduled clinic visits for reasons related to subject safety. At unscheduled visits, subjects will be queried about AEs, changes in concomitant medications, and suicidality, and safety laboratory assessments may be conducted. Periodic interim blinded review of safety data will be performed as part of routine pharmacovigilance activities. No interim statistical analysis is planned.

3.2. Study Endpoints

3.2.1 Primary Safety Endpoints

Treatment-emergent adverse events (TEAEs), treatment-related TEAEs, TEAEs leading to study discontinuation, and serious adverse events (SAEs) will be evaluated as primary safety endpoints.

3.2.2 Secondary Efficacy Endpoint

The efficacy parameters of the continuous secondary endpoints will be the mean changes from baseline in ABC-C total and subscale scores; in ABC-C factor score for FXS; in the ADAMS subscale scores; in the RBS-R total and subscale scores; in Conner's 3 subscale scores; in the Short Sensory Profile-2 total and subscale scores; and in the CGI-S and CGI-I scores.

3.2.3 Exploratory Endpoints

The exploratory efficacy endpoints are not listed in order of importance.

3.2.3.1 Caregiver-Completed Endpoints

- Change from baseline in the BASC-3 PRQ subscale scores
- Change from baseline in PGI-S and PGI-I scores
- Change from baseline in PedsQL total and subscale scores
- Change from baseline in the CHSQ total and subscale scores
- Change from baseline in sleep diary parameters, including how long it took the subject to fall asleep (sleep onset latency [SOL]), the amount of time the subject was awake during the night (WASO), the total amount of sleep obtained (total sleep time [TST]), and daytime sleepiness, defined as duration of napping in the daytime.

3.2.3.2 Clinician-Completed Endpoints

- Change from baseline in top 3 concerns visual analog scale
- Change from baseline in the VABS-3 overall composite and subscale scores
- Change from baseline in Pediatric Sleep CGI-Severity and Pediatric Sleep CGI-Improvement scores

3.2.3.3 Direct Subject Assessment Endpoints

- Actigraphy parameters for sleep, including SOL, WASO, sleep fragmentation, number of nocturnal awakenings, TST, sleep efficiency, and daily activity level.
- Mean change from baseline in KiTAP subtest scores
- Mean change from baseline in RBANS subtest scores

3.2.3.4

3.3. Treatments

OV101 is formulated as the monohydrate form (4,5,6,7-tetrahydro-isoxazolo[5,4-c]-pyridin-3-ol, monohydrate) in a white size 2 capsule. The capsule contains 5.645 mg of OV101 monohydrate, which corresponds to 5.0 mg of OV101 (Table 1).

Table 1 Pharmaceutical Composition of OV101 for the 5-mg Capsule

Component	Function	Amount (mg)
OV101 ^a	Active compound	5.645
Microcrystalline cellulose	Diluent	138.6
Magnesium stearate	Lubricant	0.725
Size 2 hard-gelatin capsule	-	60

^a Delivered as the zwitterion monohydrate. One gram of the anhydrous free zwitterion is equivalent to 1.129 g of the zwitterion monohydrate.

Placebo capsules will be identical in appearance to the capsules containing OV101 and have the same excipient ingredients but will not contain the active compound. Metrics Contract Services (Greenville, NC) will manufacture the OV101 and placebo capsules.

Subjects will take all doses orally (assisted by an LAR/caregiver, if necessary) TID (morning, afternoon, evening), at approximately the same times each day, for the duration of the 12-week treatment period. The morning and afternoon doses should be taken with light low-fat food (a glass of low-fat milk would qualify as food), and the afternoon dose should be taken at least 6 hours after the morning dose. The evening dose should be taken 30 minutes before bedtime. Capsules may be opened and the contents sprinkled onto 1 teaspoon of low-fat semiliquid food (e.g., applesauce, yogurt, pudding) for ingestion, but this approach must be followed consistently throughout the study. The capsule contents must not be placed directly in liquid. The LAR/caregiver must document specifically how each capsule was taken (e.g., swallowed whole or taken in 1 teaspoon of semiliquid food).

3.4. Dose Adjustment/Modification

There will not be any dose adjustments permitted during the study.

4. GENERAL STATISTICAL CONSIDERATIONS

All statistical analyses will be performed using SAS® Version 9.3 or higher.

All clinical study data will be presented in subject data listings. In by-treatment group descriptive presentations, the 3 randomized treatment groups will be presented separately as well as overall.

Descriptive statistics (number of subjects, mean, standard deviation (SD), median, Q1, Q3, minimum, and maximum) will be presented by treatment group for continuous variables and their changes from baseline. In addition, 95% CIs for the mean change from baseline will be provided for continuous variables. Graphical displays will be utilized to investigate trends over time and dose and the relationship between certain variables and differences between age groups. Ordinal variables with sufficient numerical categories (e.g., 7-point scales of PGI-S and CGI-S) and subscale total scores from questionnaires will be treated as continuous variables.

Categorical (not treated as continuous) endpoints (including AE incidence and binary endpoints) will be summarized by frequency and percentage. Frequencies and percentages will be presented for the shifts in these categories (e.g., low to normal, low to high, high to low) from baseline to each post-baseline assessment time point for scales with categorical variables. If there are missing values, the number missing will be presented (as a category), but without a percentage.

For all analyses, ‘Baseline’ refers as the last non-missing observation on or before the date of first dose of study medication. Change from baseline will be calculated by subtracting baseline value from post-baseline assessment for each subject.

If there are multiple records within a pre-specified visit window the non-missing visit closest to the scheduled visit day will be included in the summary tables.

The following reporting conventions apply generally to tables, listings and figures:

- All mean and median values will be formatted to one more decimal place than the measured value. Standard deviation values will be formatted to two more decimal places than the measured value. Minimum and maximum will be formatted to the same decimal as the measured value;
- All percentages will be rounded to one decimal place. The number and percentage of responses will be presented in the form xx (xx.x), where the percentage is in the parentheses. In the case the numerator is equal to the denominator, the percentage should be presented as (100) instead of (100.0). For TEAEs, the number, percentage, and event incidence will be presented in the form of xx (xx.x) [E], where E is the number of events;

- All listings will be sorted for presentation in order of randomized treatment group, study center, subject, and date of procedure or event;
- All analysis and summary tables will have the analysis population sample size for each treatment group in the column heading (i.e., number of subjects);
- P-values will be rounded to 4 decimal places. P-values that round to 0.0000 will be presented as “<0.0001” and p-values that round to 1.0000 will be presented as “>0.9999”;
- The day of first dose of study drug, OV101, will be defined as Day 1. For day calculation, if date is before first dose date then day=date - first dose date, if date is after first dose date then day=date - first dose date + 1;
- Listings of all data will identify the age group (adolescent/adult) of each subject.

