1.4 Clinical Experience with OV101

OV101 was generally safe and well tolerated in all Phase 2 and 3 studies that included more than 4300 subjects with insomnia (aged 18 to 64 years) who were administered doses up to 15 mg (20 mg in one early Phase 2 study). In adult subjects, the most common adverse events (AEs) that occurred more frequently in OV101-treated subjects than in subjects on placebo were dizziness, nausea, vomiting, somnolence, and headache. Most AEs were of mild to moderate intensity. Generally, tolerability was better in male subjects than in female subjects, most likely due to the lower body weight of females.

OV101 administration in the morning was safe at all doses (Study 99096). In healthy young men, doses up to 20 mg were well tolerated when given alone as single morning doses for 5 days. In young women, a 15 mg morning dose was not well tolerated or was tolerated with considerable discomfort from Day 2 onwards. An evening dose of 15 mg was well tolerated in young women and women above 55 years for 3 consecutive days. The AEs with the highest incidences in this study were dizziness, nausea, headache, and somnolence. The majority of AEs had a rapid onset (within 1 to 2 hours postdose) and resolved after the drug was discontinued.

Safety data from Study 11336 showed that 30 mg and 45 mg OV101 in women and 45 mg OV101 in men was not tolerated based on their history of hypnotic/sedative abuse or other drug abuse. This is contrary to previous experience with the same doses in healthy volunteers. These findings suggest that a history of hypnotic/sedative abuse or other drug abuse decreases the tolerability of supratherapeutic doses of gaboxadol. Adverse events that were associated with lack of tolerability included psychiatric events such as agitation, dissociation, hallucinations, disorientation, and anxiety.

Approximately 500 subjects were exposed to OV101 in clinical studies in non-insomnia-related development. The safety and tolerability profile of OV101 in the non-insomnia-related studies was similar to that in sleep disorder studies. In general, the AEs were dose related, with no AEs reported at the 5-mg dose and only mild AEs reported for the 10-mg dose of OV101.

Phase 2 and Phase 3 studies in adult subjects with primary insomnia demonstrated that OV101 is effective in restoring classical sleep parameters (sleep induction and sleep

Ovid Therapeutics Inc.

[figure not shown]
Protocol: OV101-17-001 Version 1.2

27 Mar 2019

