6.1.2 Baseline Visit

Screened subjects will return to the study center for the baseline (Day 1) visit. The LAR/caregiver will bring the subject's completed sleep diary and actigraph, and study staff will manage the sleep diaries and actigraphs during the visit as detailed in Section 6.1.2.1. Prior to randomized assignment of study regimen, study center staff must confirm appropriate completion of the sleep diary, proper recording of the actigraph, and fulfilment of all eligibility criteria (Section 4.1).

Subjects who meet all eligibility criteria will be randomly assigned to treatment at Baseline as described in Section 5.1. After assignment at Baseline, subjects/caregivers will receive the IWRS-assigned package of blinded study treatment according to the treatment code for the first 6 weeks of treatment.

The following schedule of activities should be observed for subjects at the baseline visit:

1. Subject should eat a light low-fat breakfast (eg , cereal with low-fat milk, bagel with low-fat cream cheese, low-fat yogurt) before coming to the clinic.
2. Study staff conduct the following assessments that involve subject participation, in the following order: Test of Attentional Performance for Children (KiTAP), Repeatable Battery for the Assessment of Neuropsychological Status (RBANS), and

3. Morning dose is administered in the clinic (study staff will record time and date). On all clinic visit days, the morning dose must be administered before noon.

4. [REDACTED]

5. Subject optionally eats a light low-fat snack.

6. [REDACTED]

Subject vital sign measurements, urine sampling, [REDACTED]

[REDACTED] can be completed at any time during the visit. The LAR/caregiver questionnaires and investigator/study staff queries of the LAR/caregiver concerning AEs, concomitant medications, and subject suicidality (Section 6.8) can also be completed at any time during the visit.

The subject and his LAR/caregiver will be expected to complete the Baseline dosing (afternoon and evening doses) and continue study drug administration for the remainder of the study.

Details of the order of activities and instructions for assessments are provided in the workbooks for caregiver/clinician/subject assessments.

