8.1.4 Conner's 3rd Edition

The Conner's 3rd Edition (Conner's 3; North Tonawanda Multi-Health System, North Tonawanda, NY) is designed to assess attention deficit hyperactivity disorder, and it will be used to collect LAR/caregiver observations of subject behavior. The assessment of behavior in neurodevelopmental disorders, such as FXS, frequently relies upon proxy report. The long form of Conner's 3 is needed to assess inconsistency (reporter reliability) and will be administered at Screening only. The short form of Conner's 3 will be administered as an outcome assessment at the baseline, Week 2, Week 6, Week 12, and EOS visits.

The Inconsistency Index/Response Style Analysis is a categorical variable obtained using two variables obtained at the Screening visit using the long form of Conner's 3: Inconsistency Index Raw Score and Inconsistency Index Number of Differentials ≥ 2 . If the Inconsistency Index Raw Score ≥ 7 and Inconsistency Index Number of Differentials ≥ 2 , then there is a possible inconsistent response style. These data will be summarized and listed.

The Raw sub scores for Content scales will be provided in the eCRF. Content scales include inattention, hyperactivity/impulsivity, learning problems, executive functioning, defiance/aggression, peer relations. The mean change of content subscale scores at Week 2,

Week 6, and Week 12 from baseline will be analyzed as described in [Section 8.1](#). Subjects with inconsistent response style at Screening visit were excluded. Missing data convention from the provider will be used for missing assessments and scores. Otherwise, missing data from the assessment will be kept as missing.

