11.2. Handling of Missing Data

If a baseline assessment is missing, then the last screening assessment close to the baseline will be used as the baseline assessment.

The maximum amount of missing data that can be tolerated and derivation of prorating subscale scores have been specified in [Section 8.1.1](#).

Last observation carried forward (LOCF) method will be applied to impute responder (binary) endpoints, including CGI-I responder, in associated sensitivity analyses (see [Section 8.1.6](#)).

For CSHQ, rule of handling missing data and the derivation of prorating domain sub scores have been specified in [Section 8.2.1.4](#).

In general, missing data convention from the provider will be used for missing assessments and scores. Otherwise, missing data from the assessment will be kept as missing (if it is not specified).

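### The SAP fixes baseline by the date of first dose, not its time, so Day 1 vital signs (and, in principle, urine and caregiver questionnaires) taken after dosing can serve as baseline

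*SAP*

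**What the plan says.** SAP section 4 defines baseline for all analyses as the "last non-missing observation on or before the date of first dose of study medication". On change scores it adds: "Change from baseline will be calculated by subtracting baseline value from post-baseline assessment for each subject". Nothing in the definition refers to clock time. The visit-window table in SAP 4.1 assigns the whole of Day 1 to Baseline.

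Protocol 6.1.2 makes Day 1 the first dosing day. Step 3 of its ordered list reads "Morning dose is administered in the clinic (study staff will record time and date", and the dose must be given before noon. KiTAP and RBANS come at step 2, before the dose. The sentence opening "Subject vital sign measurements, urine sampling" then lists items with no fixed place in the visit. It is partly redacted, but the Week 2 section (6.1.4) says the same of vital signs and urine without redaction. Caregiver questionnaires "can also be completed at any time during the visit". Protocol 3.1 makes Baseline a full-day visit and states that there is no placebo group.

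For a missing baseline, SAP 11.2 says that "the last screening assessment close to the baseline will be used as the baseline assessment", with no exception by instrument.

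**The concern.** A baseline should be free of drug. Here the rule accepts any Day 1 value, and if a subject has one before and one after the dose it picks the later one. Without a placebo group, change from baseline is the reference for the vital-sign summaries (SAP 9.3) and the urinalysis shift tables (SAP 9.2.3). The SAP also puts its emphasis on description and 95% CIs for mean change, and those intervals do not reflect a shift in the baseline itself.

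Protocol 1.4 says of one morning-dosing study: "The majority of AEs had a rapid onset (within 1 to 2 hours postdose". A full-day visit is long enough for effects on that time scale to reach a Day 1 measurement.

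A second weakness lies in the fallback. Conners 3 is given as the long form at Screening and as the short form at Baseline and every outcome visit (SAP 8.1.4). If a Day 1 short form is missing, SAP 11.2 points to Screening, and a raw content-scale change could then span two forms.

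**Working it through.** **The plan's own figure.** The only numeric design figure is the 13.9% half-width for a 20% TEAE incidence at N = 30 (SAP 4.2). Wilson half-width = [z/(1 + z²/n)]·√[p(1−p)/n + z²/(4n²)]. With z = 1.96, n = 30 and p = 0.20 this is (1.96/1.128)·√(0.005333 + 0.001067) = 0.139, with interval 9.5% to 37.3%. It reproduces and does not depend on the baseline definition. Nor does the enrolment figure: 30/(1 − 1/6) = 36.

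**Inputs for the bias.** None of these values is in the documents.
- a: acute post-dose effect on the measure, taken as equal on Day 1 and at follow-up
- f: share of Day 1 baseline values taken after the dose
- g: share of follow-up values taken after that day's clinic dose
- s: any sustained effect present before that day's dose

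**Formula.** Mean follow-up value = true baseline + s + g·a. Mean recorded baseline = true baseline + f·a. Therefore:
- current rule: mean change = s + (g − f)·a
- pre-dose baseline (f = 0): mean change = s + g·a
- difference: −f·a, whatever g is

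**Acute part left in the change score, (g − f)·a, over assumed ranges:**

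| f | g = 0 | g = 0.5 | g = 1 |
|---|---|---|---|
| 0 | 0 | 0.5a | 1.0a |
| 0.25 | −0.25a | 0.25a | 0.75a |
| 0.5 | −0.5a | 0 | 0.5a |
| 0.75 | −0.75a | −0.25a | 0.25a |
| 1 | −1.0a | −0.5a | 0 |

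The acute part vanishes only when f = g. At g = 1, f of 0.25 to 0.75 removes 25% to 75% of it. At g = 0.5 the same range removes 0.25/0.5 = 50% to 0.75/0.5 = 150%, and above 100% the sign reverses. At Week 2, Week 6 and EOT, subjects arrive before their morning dose and vital signs may again be taken before or after it, so g is open. At EOS, 4 to 6 weeks after EOT, g is 0 for subjects who took their last dose at EOT, and the acute part of the change is −f·a.

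**Which measures are exposed.**
- Vital signs: due on Day 1 in every case, since they are not among the procedures that may be skipped when Screening is within 10 days. Fully exposed.
- Urinalysis: exposed only if Day 1 laboratory tests are repeated. The documents describe no acute urinary effect.
- Caregiver questionnaires: exposed in principle, but a dose that morning should matter little where the instrument looks back over a period. CSHQ recalls the preceding week (SAP 8.2.1.4).
- CGI-S and other clinician ratings: their place relative to the dose is not stated.
- KiTAP and RBANS: ordered before the dose. Not exposed.
- Sleep diary and actigraphy: taken from the 7 days before Day 1. Not exposed.

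**Between-arm differences.** Every arm takes the same 5 mg morning capsule on Day 1 (Protocol Table 5-2), so −f·a has the same expectation in each arm and drops out of contrasts. This assumes similar assessment timing across arms and no assessment after the afternoon dose, which comes at least 6 hours later.

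**Screening fallback.** In Protocol Table 6-1, vital signs, laboratory tests, CGI-S and PGI-S are taken at Screening. ABC-C, ADAMS, RBS-R, Short Sensory Profile-2, CSHQ, PedsQL, VABS-3 and the top-3-concerns VAS are not.

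**The case against.** The case against giving this much weight is substantial, and most of it limits the size of the problem.

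- The rapid-onset statement comes from a study with morning doses up to 20 mg and concerns dizziness, nausea, headache and somnolence, not vital signs or urine. Protocol 1.4 also reports no AEs at 5 mg in the non-insomnia studies, and good tolerability of a 5-mg morning dose in adolescents with FXS or Angelman syndrome. This stands: a may be small.
- The primary endpoints are TEAEs, related TEAEs, TEAEs leading to discontinuation and SAEs. They are judged against the state before exposure, not against the SAP section 4 baseline. A reader might infer that the primary safety analysis is biased; the documents do not support that.
- A reader might also infer that acute effects simply cancel out of the change scores. That needs f = g, and the documents fix neither.
- Table 6-1 shows one Day 1 vital-signs entry, so a subject with both a pre-dose and a post-dose value is hypothetical. The single value may still be post-dose.
- The workbooks, which are not among the documents, may set an order. That could reduce f in practice, but the SAP definition would still accept a post-dose value.
- On Conners 3, SAP 8.1.4 keeps missing data as missing unless the provider's convention applies, and it uses the Screening form only for inconsistency. The documents do not say whether long-form content scores reach the eCRF. The mismatch is therefore rare, but SAP 11.2 does not exclude it.

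Replacing every post-dose Day 1 value with Screening would do harm: most secondary questionnaires have no Screening value, so those subjects would lose their change scores.

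**Conclusion.** The gap is real and worth closing, mainly for vital signs. As written, the SAP accepts drug-exposed Day 1 values as baseline, and within-arm and overall mean change then shift by −f·a. With assumed f of 0.25 to 0.75, that is 0.25a to 0.75a in size. The result rests on a being alike on Day 1 and at follow-up; f, g and a are all absent from the documents, so no absolute size can be given.

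Urinalysis and caregiver questionnaires are exposed in principle, with little expected effect. The point does not extend to KiTAP, RBANS, sleep diary, actigraphy, the primary TEAE endpoints or expected between-arm differences, and no design figure moves. The Conners 3 form mismatch is a separate, rare gap in the same baseline rules.

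**What to change.** 1. **Protocol 6.1.2.** Complete Day 1 vital signs, urine sampling and caregiver questionnaires before the in-clinic dose, and record the time of each. Dose time is already recorded; the documents do not say that assessment times are.
2. **SAP section 4.** Define baseline as the last non-missing value before the date and time of first dose. For a Day 1 value that is post-dose or untimed, use Screening only where the same measure was taken then (for example vital signs, laboratory tests, CGI-S, PGI-S). For questionnaires with no Screening assessment, keep the Day 1 value, flag it, and run a sensitivity analysis excluding values not shown to be pre-dose.
3. **SAP sections 4 and 11.2.** Exclude Conners 3 from the Screening fallback, so that a missing Day 1 short form stays missing.

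The cost is an ordering constraint on a full Day 1 visit, an assessment-time field, and some subjects with a Screening baseline for vital signs that may be up to 21 days old. If the pre-dose order is followed and times are recorded, that last group should be small.
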